The first line systemic therapy for psoriasis is methotrexate. Ciclosporin, acitretin and biologic agents are alternatives if methotrexate is not appropriate or successful. Methotrexate is an antineoplastic antimetabolite with anti-inflammatory and immunosuppressant properties. The exact mechanism of action remains unclear and it is likely that different dosing regimens have different biological effects. The low dose weekly regimen used for psoriasis treatment may work by increasing the level of anti-inflammatory proteins called adenosines or by an effect on cell division due to inhibition of the tetrahydrofolate reductase enzyme. At higher doses, used in chemotherapy regimens, methotrexate works by causing significant inhibition of tetrahydrofolate dehydrogenase and prevents the formation

of tetrahydrofolate, which is necessary for the formation of thymidylate an essential component of DNA. Methotrexate is used in many conditions including psoriasis, psoriatic arthritis, rheumatoid arthritis and Crohn's disease. In chronic plaque psoriasis 50-60% of patients treated with methotrexate see a reduction in PASI score of 75% in 3-6 months¹⁰.

Since the early days of methotrexate treatment for psoriasis there have been concerns regarding liver toxicity. However, a number of confounding factors have always made it unclear whether or not the methotrexate was responsible for the liver fibrosis identified in some patients.

Due to the concerns regarding liver fibrosis and methotrexate the early guidelines recommended pre-treatment liver biopsy and then repeat liver biopsy for every 1.5g cumulative methotrexate. As the use of methotrexate became more widespread the enthusiasm for routine liver biopsies decreased. Data also emerged showing that the development of significant liver fibrosis was highly unlikely with less than 5g cumulative methotrexate⁸.

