Fibrotic livers have reduced elasticity due to the deposition of fibrous tissue in the hepatic parenchyma. TE gives a 'liver stiffness measurement' (LSM) using pulsed-echo ultrasound as a surrogate marker of fibrosis. The LSM correlates well with the degree of hepatic fibrosis in a range of liver diseases, including NAFLD, hepatitis B, hepatitis C and in patients treated with methotrexate²². In a study of 246 patients with biopsy-proven NAFLD, TE achieved high AUROCs for the detection of \geq stage 2 fibrosis, \geq stage 3 fibrosis and cirrhosis (0.84, 0.93 and 0.95, respectively) and performed better than a number of simple non-invasive scores in the staging of fibrosis. In that study, TE had a high NPV of 96% for \geq stage 3 fibrosis at a cut-off of 7.9 kPa but only modest PPV (52% at 7.9 kPa and 72% at 9.6 kPa)²³. A low LSM reliably excludes advanced fibrosis, but the optimum cut-offs for clinical use are yet to be determined. Previous observational studies looking at the prevalence of liver fibrosis and advanced liver fibrosis used LSM >7 kPa and LSM >9.5 kPa as their cut-off values³⁻⁵. However, there are significant limitations to using TE. Results may be invalid in those with central obesity (BMI >35 kg/m²) or type 2 diabetes²⁴. For obese patients, the Fibroscan XL probe has been developed that is associated with fewer LSM failures (1.1% vs16%) than the M probe and was accurate for the diagnosis of \geq F2 fibrosis and cirrhosis (AUROC 0.83 and 0.94, respectively)²⁵. However, even with the XL probe, 10% of patients with a BMI >28 kg/m² have a difference of ≥ 2 fibrosis stages between TE and liver biopsy²⁶.

Despite its limitations, the usefulness of TE in detecting liver fibrosis in patients with psoriasis has been demonstrated and TE is increasingly recommended to be used in monitoring patients taking methotrexate ^{4, 21}.

9. Objectives

Primary objective To determine the prevalence of liver fibrosis in patients with psoriasis (LSM >7.9kPa, >7.0 kPa, > 9.5kPa) and to evaluate the relationship between the cumulative dose of methotrexate and liver fibrosis in patients with psoriasis.

Secondary objectives

1. To evaluate the relationship between other liver fibrosis risk factors and non-invasive markers of liver fibrosis in patients with psoriasis using univariate analysis.

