11.6. Sampling strategy

Total sample size: 250 (can be increased to up to 500).

As this is a pilot study, this should be an adequate sample to test recruitment and the estimate effect sizes to include in a formal statistical power calculation for a planned larger study.

We are interested to recruit a mix of patients receiving different types of treatment including phototherapy and biologics. We will aim to recruit at least 100 patients who are receiving or have previously received methotrexate.

We will compare our study population to BADBIR population to ensure we demonstrate that our sample is representative.

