11.13. Analysis Methods

All of the data will be assembled in a spreadsheet that will be designed and checked by our statistical collaborators.

The analysis will be performed including all patients and then the group will be divided based on the PASI score (PASI >10 and PASI <10) and analysis of the separate groups will be performed.

We will calculate the prevalence of liver fibrosis (the proportion of the population affected by liver fibrosis) by dividing the number of participants with liver fibrosis in the study population by the total number of people in study population.

For the analyses we will perform these 3 times using the 3 different cut off values for liver stiffness measurements of 7Kpa, 7.9Kpa and 9.5Kpa. There is currently no consensus as to which value is most appropriate. We will therefore analyse using all three.

Regression analyses will be carried out, the results of which will be used to inform a power calculation for future research.

- Logistic regression will be used to consider the association between liver fibrosis (yes/no) and methotrexate dose (continuous).
- Linear regression will be used to consider level of liver fibrosis (continuous i.e. independent of cut offs) and methotrexate dose (continuous).
- Regression models will also be used to investigate the relationship between other risk factors (e.g. BMI, waist circumference, alcohol consumption etc.) and liver fibrosis.

Analysis will be carried out in STATA 15.

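### On its ordinary reading, the planned methotrexate slope blends the ever/never contrast with the per-gram trend among users, so a within-user estimate and a linearity check should be reported beside it

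*Protocol*

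**What the plan says.** The primary objective (sections 6 and 9) has two parts: the prevalence of liver fibrosis, and "to evaluate the relationship between the cumulative dose of methotrexate and liver fibrosis in patients with psoriasis". Section 11.13 sets out how the second part is analysed.

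- Binary outcome: "Logistic regression will be used to consider the association between liver fibrosis (yes/no) and methotrexate dose (continuous").
- Continuous outcome: "Linear regression will be used to consider level of liver fibrosis (continuous i.e. independent of cut offs) and methotrexate dose (continuous").
- Analysis set: "The analysis will be performed including all patients and then the group will be divided based on the PASI score".

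Section 11.13 mentions no ever-use term, no analysis restricted to methotrexate users and no check of the shape of the dose relation. It says the regression results will inform a power calculation for later research. Section 7 describes the analysis of the measured risk factors, cumulative methotrexate dose among them, as univariate.

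Section 11.6 gives the sample: "Total sample size: 250 (can be increased to up to 500"). It continues: "We are interested to recruit a mix of patients receiving different types of treatment including phototherapy and biologics", and "We will aim to recruit at least 100 patients who are receiving or have previously received methotrexate". Section 8 reports that significant fibrosis was "highly unlikely with less than 5g cumulative methotrexate".

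**The concern.** Patients who never took methotrexate have a cumulative dose of exactly zero. In a model with one dose term, they and the users determine the slope together. That slope answers two questions at once: do ever-users differ from never-users, and among users, does liver stiffness (LSM) rise with each further gram?

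The first comparison is the more exposed to selection. Section 8 says the alternatives are used where methotrexate is unsuitable or has failed, and section 11.9 recruits from phototherapy and PUVA clinics as well as drug-monitoring clinics. Never-users may therefore differ from users in liver risk or disease severity, and a univariate model adjusts for neither.

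Two errors are possible. A difference between users and never-users that has nothing to do with dose can appear as a dose-response. A real trend among users can be diluted or masked by the way never-users were selected. Either would affect a primary objective and pass into the later power calculation.

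**Working it through.** The protocol gives no effect size, standard deviation or dose distribution, so there is no planned figure to reproduce. Dose variability and the simulation settings below are assumptions.

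**1. Zero-dose share (section 11.6).** At most (250 − 100)/250 = 60%. At the permitted 500 with the same floor, (500 − 100)/500 = 80%. Both are ceilings, because the floor is a minimum number of users.

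**2. What one slope estimates.** Let p be the share of ever-users, m and s the mean and SD of dose among users, and CV = s/m. Per patient, the dose variation within users is p·s² and that between users and never-users is p(1 − p)·m². Least squares then gives

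slope = w × (ever/never mean difference ÷ m) + (1 − w) × (slope among users), with w = (1 − p)/(CV² + 1 − p).

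The weight w of the ever/never contrast is:

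| Zero-dose share | CV 0.75 | CV 1.0 | CV 1.25 |
|---|---|---|---|
| 60% (p = 0.4) | 0.6/1.1625 = 0.516 | 0.6/1.6 = 0.375 | 0.6/2.1625 = 0.277 |
| 20% (p = 0.8) | 0.2/0.7625 = 0.262 | 0.2/1.2 = 0.167 | 0.2/1.7625 = 0.113 |

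The identity is exact for the linear model. In the logistic model the same mixing occurs, but these weights do not apply exactly.

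**3. Dilution.** If selection made the ever/never difference exactly zero, the reported slope would be (1 − w) of the slope among users. At p = 0.4 that is 0.484 for CV 0.75 and 0.723 for CV 1.25. This is an illustration, since the documents give no size for that difference.

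**4. Simulation.** Assumed inputs: 2,000 runs, 250 patients, 100 users, gamma-distributed doses with mean 3 g, CV 0.5 to 1.0, residual LSM SD 2.5 kPa.

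| True relation | Single term: mean slope (kPa/g) | Single term: significant | With ever-use indicator: mean slope | With indicator: significant |
|---|---|---|---|---|
| 1 kPa step for ever-use, no dose effect | 0.13 to 0.24 | 48% to 74% | 0.00 | 5% to 6% |
| Linear through zero, 0.3 kPa/g | about 0.30 | 92% to 98% | about 0.30 | 44% to 92% |
| Effect only above 5 g, 0.5 kPa/g | 0.04 to 0.18 | 8% to 73% | 0.10 to 0.24 | 10% to 76% |

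The first row agrees with step 2: at CV 1.0, 0.375 × 1/3 = 0.125 kPa/g, against 0.13 simulated.

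The rows show three things. A pure ever/never step can pass as a dose-response under the single term, and the indicator prevents this. If the relation really is linear through zero, the single slope is unbiased and clearly more powerful. If the effect begins only above some dose, the indicator alone does not recover it, so a separate check of shape is needed.

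**The case against.** The strongest reply is that section 11.13 fixes only the scale of dose. Calling it continuous means it will not be categorised; it does not exclude an indicator, a spline or a linearity check, and a statistical analysis plan not shown here may add them. That is correct as far as it goes: a commitment to one straight-line term is an inference. It is nevertheless the ordinary reading of a univariate model with a continuous exposure in all patients, and section 11.13 does name the models and the analysis set.

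Second, zero is a legitimate cumulative dose, and the objective concerns patients with psoriasis, not only methotrexate users. This stands. It is why the planned model should be kept, and why the within-user trend cannot be called the only quantity of interest.

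Third, the real share at zero may be well below 60%, since section 7 says most patients needing systemic therapy try methotrexate first. This also stands. At 20% zero dose the weight falls to 0.17 at CV 1.0, which is smaller but not negligible.

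Fourth, the study is a pilot, and the question of independent risk is deferred to a larger study. That lowers the stakes, but the estimates from this study are meant to size the next one.

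Finally, a within-user slope is not free of confounding, because dose among users can itself follow severity or tolerance. This is true; the proposal removes only the ever/never component.

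**Conclusion.** The point holds as a needed addition to section 11.13. It does not show that the planned model is wrong. On the ordinary reading, between about 17% (20% at zero dose, CV 1.0) and 52% (60% at zero dose, CV 0.75) of the weight in the reported slope comes from the ever/never contrast. These figures rest on assumed CVs and on a zero-dose share that the protocol bounds but does not predict. Mixing does harm only if users and never-users differ for reasons other than dose, or if the relation is not linear through zero.

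A reader might infer more than the documents support:

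- **That 60% of patients will have zero dose.** It is a ceiling derived from a recruitment floor.
- **That the background contradicts linearity.** The statement about 5 g, and the 8% risk cited at 6 g in section 8, concern fibrosis as a yes/no finding. They give reason to check the shape but establish no threshold for mean LSM. A logistic model linear in dose already allows risk to stay low and then climb.
- **That the slope will be cut to 48% to 72% of its true value.** That requires an ever/never difference of exactly zero as well as the assumed CVs.
- **That its sign will be reversed.** At p = 0.4 this needs an ever/never contrast, per gram of mean user dose, of opposite sign and more than (1 − w)/w times the within-user slope: 0.484/0.516 = 0.94 times at CV 0.75, and 0.723/0.277 = 2.6 times at CV 1.25. Nothing in the documents points to a contrast of that size.

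**What to change.** Keep the all-patient models in section 11.13 and state there that each will be reported beside:

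- **A within-user estimate:** a model with an ever-use indicator plus cumulative dose, or the same dose model in ever-users only, with the ever/never difference given separately. In the linear model both routes give the same dose coefficient.
- **One pre-stated non-linearity check of dose:** for example, a restricted cubic spline.

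Add that a dose-response will be interpreted, and carried into the future power calculation, only in light of the within-user estimate.

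No new data are needed, since cumulative dose is already on the case report form. The cost is some extra analysis and a wider interval for the within-user slope. Under the assumed inputs, power for the dose term falls from 92%–98% to 44%–92% if the truth is linear through zero. That loss is why the new model supplements the planned one and does not replace it.

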Number of study sites	One (the Newcastle upon Tyne Hospitals NHS Foundation Trust)
Study population size	250
Study duration	2 years

7. Introduction

Patients with psoriasis appear to have higher rates of liver fibrosis in comparison to the general population. The higher rates of risk factors for liver fibrosis such as obesity, alcohol and diabetes are important; however there have been concerns that methotrexate can contribute to liver fibrosis. Ever since methotrexate has been used to treat psoriasis there have been concerns over the risk to liver health. Until the 1990s liver biopsies were recommended pre and during MTX therapy. Despite the increasing importance of biologic therapies, methotrexate remains the most commonly used systemic agent in the UK. The majority of patients needing systemic therapy will try methotrexate first as per NICE guidance.

This study aims to investigate the prevalence of liver fibrosis in a group of patients with psoriasis by measuring liver stiffness measurement (LSM) using Transient Elastography (TE), now increasingly used for monitoring of liver fibrosis. The previous standard to monitor liver fibrosis was liver biopsy but concerns over morbidity and mortality along with sampling error have led to a decline in this test being performed. In addition to measuring liver stiffness, the cumulative methotrexate dose and other important factors including BMI, waist circumference and alcohol intake will be recorded. A univariate analysis will be performed to investigate the relationship between all measured risk factors and LSM.

The ultimate goal is to use the prevalence data to perform a power calculation to determine the number of participants required to conduct a study to determine which factors can predict the risk of liver fibrosis. Increasingly experts believe that other risk factors for liver fibrosis such as obesity and alcohol intake may be more important than methotrexate. We want to determine whether or not methotrexate is an independent risk factor for liver fibrosis in patients with psoriasis and if so whether we can predict which populations are most at risk from negative side effects of methotrexate. Using this data a risk prediction model can be built to allow optimal and safe prescribing of methotrexate.

8. Background

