- NAFLD and Fib4 score will be calculated and metabolic syndrome will be assessed based on the IDF metabolic syndrome definition (modified version will be used when fasting results not available (fasting glucose will be replaced by HBA1C and HDL cholesterol and Triglyceride will be replaced by non-fasting value)

A modified the definition will be used: a non-fasting lipid profile when fasting values are not available or HBA1C will be used when fasting glucose is not available.

https://www.uptodate.com/contents/image?imageKey=ENDO%2F53446&topicKey=PC%2F1784&search=metabolic%20syndrome&rank=1~150&source=see_link

Metabolic syndrome	
	IDF 2006 definition
Required	Waist \geq 94 cm (men) or \geq 80 cm (women)
	And \geq2 of:
Glucose	\geq 5.6 mmol/L (100 mg/dL) or diagnosed diabetes
HDL cholesterol	$<$ 1.0 mmol/L (40 mg/dL) (men); $<$ 1.3 mmol/L (50 mg/dL) (women) or drug treatment for

	low HDL cholesterol
Triglycerides	≥1.7 mmol/L (150 mg/dL) or drug treatment for high triglycerides
Hypertension	≥130/85 mmHg or drug treatment for hypertension
	¶ For South Asia and Chinese patients, waist ≥90 cm (men) or ≥80 cm (women); for Japanese patients, waist ≥90 cm (men) or ≥80 cm (women).

This observational study does not impact patient treatment and has no risk of causing adverse events.

11. Concept

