History of excessive alcohol consumption:	Yes/No
>35 units/week (females), >50units/week (males)	Yes/No
>14units/day (female/male)	Yes/No
History of alcohol dependence?	Yes/No

Comorbidities	Yes/no (0/1), year of onset
Cardiac disease	
Heart failure	
Cardiac arrhythmias	
Stroke	
Coronary artery disorders	
Angina	
Myocardial infarction	
Vascular diseases	
Hypertension	
Peripheral vascular disorders	
Deep vein thrombosis	
Pulmonary embolism	
Disorders of metabolism and nutrition	
Diabetes mellitus	Type I/II
Impaired glucose tolerance	
Dyslipidaemia	
Endocrine diseases	
Thyroid disease	
Nervous system disorders	
Demyelinating diseases	
Epilepsy	
Respiratory, thoracic and mediastinal disorders	
Asthma	
COPD	
Renal and urinary tract diseases	
Chronic renal failure	
Hepatobiliary diseases	
Viral hepatitis infection	
Other liver disease	
Gastrointestinal diseases	
Peptic ulcer	
Gastrointestinal inflammatory conditions	
Crohn's disease	
Ulcerative colitis	
Psychiatric diseases	
Depression	
Anxiety	
Infections and infestations	

Tuberculosis	
Immune system disorders	
Skin and soft tissue disorders	
Psoriatic arthritis	
Diagnosis of PSA by a rheumatologist?	
Year of diagnosis	
Other types of cancers	
Skin cancers	
Non-melanoma skin cancer	
Squamous cell carcinoma	
Basal cell carcinoma	
Melanoma skin cancers and pre-cancerous skin lesions	
Melanoma skin cancer	
Melanoma in situ	
Bowen disease	
Actinic keratosis	
Keratoacanthoma	

UV therapy	No of course, no of treatments, cumulative dose (J/cm ²), date known to be accurate
Broadband UVB	
Narrowband UVB	
Total Body PUVA	
Oral Puva	
Topical Puva	
Hand and Foot PUVA	
Oral PUVA	
Topical PUVA	

Medications	
Methotrexate	
Cumulative dose	gram
Duration	Months
Folic acid	Years & Frequency
Other systemic drugs and biologics	Start dates
Ciclosporin	years
Acitretin	years
Apremilast	
Dimethyl fumerate	
Adalimumab	Years
Etanercept	Years
Ustekinumab	
Secukinumab	
Infliximab	
Other biologics	

Other DMARDS	
Drug treatment for low HDL cholesterol/or raised triglycerides	*For metabolic syndrome definition
Drug treatment for diabetes	*For metabolic syndrome definition
Patients current medications	Date started

Blood tests	
HBA1C	
Lipid profile	
Triglycerides	
HDL	
LDL	
Cholesterol	
Platelets	
Liver function tests	
ALT	
Worse every ALT in the past year	
AST	
Worse every AST in the past year	
ALT/AST ratio	
Albumin	
Procollagen three peptide (PIIINP) – worse value	

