Fib 4 score	https://www.mdcalc.com/fibrosis-4-fib-4-index-liver-fibrosis
AST	
ALT	
Platelets	
Age	

NAFLD score	https://www.mdcalc.com/naflid-non-alcoholic-fatty-liver-disease-fibrosis-score
BMI	
Impaired fasting glucose/Diabetes	
ALT	
AST	
Platelet count	
Albumin	

Metabolic syndrome	
	IDF 2006 definition
Required	Waist \geq 94 cm (men) or \geq 80 cm (women)
	And \geq2 of:
Glucose	\geq 5.6 mmol/L (100 mg/dL) or diagnosed diabetes
HDL cholesterol	<1.0 mmol/L (40 mg/dL) (men); <1.3 mmol/L (50 mg/dL) (women) or drug treatment for low HDL cholesterol
Triglycerides	\geq 1.7 mmol/L (150 mg/dL) or drug treatment for high triglycerides
Hypertension	\geq 130/85 mmHg or drug treatment for hypertension
	¶ For South Asia and Chinese patients, waist \geq 90 cm (men) or \geq 80 cm (women); for Japanese patients, waist \geq 90 cm (men) or \geq 80 cm (women).

Description	Fitzpatrick skin type
Burns easily, never tans	1
Burns easily, tans minimally	2
Burns moderately, tans gradually	3
Burns minimally, tans well	4
Rarely burns, tans profusely	5
Never burns, deeply pigmented	6

Patient baseline questionnaire

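### The univariate models for waist, HDL and alcohol pool men and women without a sex term, so the slopes passed to the future power calculation may be biased in either direction

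*Protocol*

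**What the plan says.** Section 11.13 (Analysis Methods) states: "Regression models will also be used to investigate the relationship between other risk factors (e.g. BMI, waist circumference, alcohol consumption etc.) and liver fibrosis". It names no covariate. On subgroups it says: "The analysis will be performed including all patients and then the group will be divided based on the PASI score", and no split by sex appears.

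The form of these models is fixed elsewhere. Section 7 (Introduction) states: "A univariate analysis will be performed to investigate the relationship between all measured risk factors and LSM". Secondary objective 1, in sections 6 and 9, reads: "To evaluate the relationship between other liver fibrosis risk factors and non-invasive markers of liver fibrosis in patients with psoriasis using univariate analysis". Section 7 covers all measured risk factors, so it takes in HDL, which section 11.13 does not name.

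Several of these factors have sex-specific limits in the protocol:

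- **Waist:** the metabolic syndrome table (section 10, and again in the Case Report Form) requires at least 94 cm in men and 80 cm in women.
- **HDL:** the same table uses "<1.0 mmol/L (40 mg/dL) (men); <1.3 mmol/L (50 mg/dL) (women").
- **Alcohol:** one history item uses ">35 units/week (females), >50units/week (males"). Another uses a single limit of more than 14 units/day for both sexes.

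Section 11.13 adds that the regression results will inform a power calculation for future research. Section 20 of the sampling text is not involved; section 11.6 describes the study as a pilot meant to supply effect sizes for that calculation.

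**The concern.** The protocol allows for sex when it classifies waist, HDL and sustained heavy drinking. It states no allowance for sex when it estimates how these factors relate to liver stiffness. A one-variable model over men and women together mixes two things: the change in stiffness with the factor within each sex, and any difference between the average man and the average woman. The second part contaminates the slope whenever sex is linked both to the factor and to stiffness at a given value of the factor.

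What is at stake is the effect size handed on. The later study is to be multivariable. If its model includes sex (likely, but not stated), the effect it must be powered for is the within-sex one. A pooled slope that is too small would make that study larger than needed, and one that is too large would leave it underpowered.

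**Working it through.** The protocol gives no effect size, SD, alpha or power for these models, and 250 is stated without a calculation. There is no figure to reproduce, and this point does not dispute the sample size. The question is how far a pooled slope can lie from the within-sex slope.

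**Inputs from the protocol:** waist thresholds 94 and 80 cm, a gap of 14 cm (the table's footnote gives 90 and 80 cm for some ethnic groups).

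**Assumed inputs:** share of men p = 0.5 to 0.6; within-sex SD of waist s = 12 to 16 cm; male-female mean difference d = 4 to 14 cm; the same slope b in both sexes.

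**Formula.** Let log LSM = b × waist + h × (1 if male) + error. Then

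- pooled slope / within-sex slope = 1 + (h/b) × K, with K = p(1−p)d / (s² + p(1−p)d²).

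A model that includes sex recovers b whatever h is.

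**Case A: risk follows distance above the sex-specific threshold.** Here h = −14b, so the ratio is 1 − 14K.

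- p = 0.5, s = 12, d = 14: K = 3.5/193 = 0.0181; ratio 0.746.
- p = 0.6, s = 16, d = 4: K = 0.96/259.84 = 0.0037; ratio 0.948.

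The pooled slope is about 5% to 25% too small.

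**Case B: risk follows raw centimetres, and men have log LSM higher by g at equal waist.** Take b = 0.01 per cm, p = 0.5, s = 14; the ratio is 1 + (g/b)K.

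- g = 0.1, d = 8: K = 2/212 = 0.0094; ratio 1.09.
- g = 0.2, d = 12: K = 3/232 = 0.0129; ratio 1.26.

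The pooled slope is about 9% to 26% too large.

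**Case C: risk follows raw centimetres and sex has no effect of its own.** Here h = 0 and the ratio is 1.00.

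**Logistic check of Case A.** In a simulation of 400,000 subjects (event rate about 11%, p = 0.5, d = 14), the odds ratio per 10 cm was 1.34, 1.29 and 1.26 pooled against 1.47, 1.36 and 1.31 with sex included, for s = 12, 15 and 18 cm.

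**HDL and alcohol under Case A, with mean gap equal to threshold gap and p = 0.5.** The ratio becomes s²/(s² + 0.25 × gap²).

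- HDL, gap 0.3: 0.09/0.1125 = 0.80 (s = 0.3) to 0.25/0.2725 = 0.92 (s = 0.5).
- Alcohol, gap 15: 100/156.25 = 0.64 (s = 10) to 1600/1656.25 = 0.97 (s = 40). This is the weakest illustration, because the gap comes from a history cut-off and not from mean intake.

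**Effect on a future sample size.** In Case A with d = 14 and p = 0.5, the correlation shrinks by the square root of the ratio. The number needed therefore grows by its inverse: 1/0.746 = 1.34, 1/0.821 = 1.22 and 1/0.869 = 1.15 for s = 12, 15 and 18. In Case B the error runs the other way.

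**Set against sampling error.** In Case A a within-sex correlation of 0.30 falls to about 0.26 to 0.29. With 250 patients its standard error is about (1 − 0.09)/√249 = 0.058, and the 95% interval is about 0.18 to 0.41. The shift is below one standard error.

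**The case against.** The strongest reply is that the protocol openly declares a univariate analysis for a pilot, that the coding of covariates is normally left to an analysis plan, and that unadjusted estimates are unadjusted by design. The part about coding stands. The protocol says continuous only of methotrexate dose and of the level of fibrosis. A reader might infer that waist, HDL and alcohol must enter in raw units, but this is not stated. The Case Report Form records waist in cm and alcohol in units per week, which suggests it and no more. The absence of a sex term is different: univariate is the wording of a stated objective, so an analysis plan that added sex would depart from it.

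Three stronger readings are tempting and unsupported.

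- **That the thresholds prove the slopes are distorted.** The waist and HDL limits are components of a metabolic syndrome definition. They do not say that liver stiffness is equal at 94 cm in men and 80 cm in women. Case C shows there may be no bias at all.
- **That every one of these factors has only a sex-specific limit.** Alcohol also has a limit common to both sexes, and the 35/50 item concerns a history of sustained excess, separate from average intake in the last year.
- **That the ranking of waist against BMI would be upset.** BMI classes are indeed the same for both sexes in the Case Report Form, but no ranking is planned here. Finding the most important factors is attached to the later multivariable study (secondary objective 2). Per SD, the scale on which factors would be compared, the waist loss is also smaller: a correlation ratio of 0.86 to 0.93 for s = 12 to 18 cm in Case A with d = 14.

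It also stands that the size and sign of any bias rest wholly on figures the protocol does not give.

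**Conclusion.** The concern holds in a limited form. As written, the plan yields sex-unadjusted slopes for waist, HDL and alcohol and passes them to a power calculation for a multivariable study. Those slopes may be biased, in a direction that cannot be told in advance. For waist the illustration runs from 5% to 25% too small to 9% to 26% too large, with zero bias if risk follows raw centimetres and sex has no effect of its own. The SDs, sex mix, mean differences, slope and sex effect are all assumed. The case is firmest for waist and HDL and weaker for alcohol. The likely shift is smaller than the sampling error of a pilot of 250, so this is minor: a cheap improvement to the stated method, not an error that invalidates it.

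**What to change.** Add one sentence to section 11.13: for waist circumference, HDL and alcohol intake, an estimate with sex as a covariate will be reported beside the univariate estimate, and the sex-adjusted estimate will be used for the power calculation. Secondary objective 1 can keep its univariate wording if the second estimate is named as an addition.

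Do not instead recode these factors as distance from a diagnostic threshold. That is not equivalent to adjusting for sex and can add bias. In Case B with d = 8, recoding changes the mean difference to 8 − 14 = −6 cm and the sex term to g + 14b. The ratio is then 1 + (14 + g/b) × (−1.5/205):

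- g = 0: 0.90, where the raw pooled slope was already correct at 1.00.
- g = 0.1: 0.82, against 1.09 raw.
- g = 0.2: 0.75, against 1.19 raw.

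The cost is one degree of freedom per model and a second estimate that is not strictly univariate. Sex is already collected. At the 11% prevalence cited in section 8 for LSM above 7 kPa, 250 patients give about 27.5 cases, or roughly 14 per slope in a two-term logistic model. The PASI subgroups will have fewer, so there the adjusted logistic estimates will be less stable.
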